**How does dysphagia assessment in acute stroke affect pneumonia?**

**Statistical Analysis Plan**

## Statistical Analysis Plan

### Research background

Stroke-associated pneumonia (SAP) is a common post stroke infection affecting 14% of patients (Kishore et al. 2015) and is associated with an increased risk of hospital mortality (Westendorp et al. 2011) and prolonged hospital stay (Finlayson et al. 2011). The combination of stroke-induced immune-deficiency and aspiration of oropharyngeal secretions and gastric contents into the lungs secondary to impaired consciousness and dysphagia predisposes patients to SAP in the first few days post stroke (Hannawi et al. 2013). Patients with dysphagia with confirmed aspiration have an 11-fold increased risk to SAP (Martino et al. 2005). However, up to half of patients with SAP do not aspirate (Westendorp et al.), which reflects SAP's multifactorial pathophysiology.

There is wide variation in the assessment and management of dysphagia in acute phase stroke and there is the potential for a range of medical interventions and clinical processes to be associated with risk of SAP (Eltringham et al. 2018, 2019). This research aims to find out how methods of dysphagia assessment and clinical management during the first 72 hours of admission to hospital affect the risk of stroke patients developing SAP and what care processes and interventions specific to patients with dysphagia affect the risk of stroke patients developing SAP during acute phase stroke.

### Research question

How does variation in assessment and management of dysphagia in acute stroke affect development of stroke-associated pneumonia?

## Hypotheses and rationale

**Hypothesis 1 - *There is no difference in incidence of pneumonia using a dysphagia screening protocol that uses 100% water compared to a dysphagia screening protocol that uses water and other consistencies (Null hypothesis)***

There are a range of dysphagia screening tools used and different methods of evaluation (Eltringham et al. 2018). Some hospitals used standardised screens; others use local dysphagia screening protocols (Eltringham et al. 2019). Some dysphagia screens evaluate patient characteristics and do not involve screening the patient with any water or food, some screens involve water only and others screen with water and different fluid and or diet consistencies. UK Clinical Guidelines state there is good evidence that a multi-item dysphagia screening protocol that includes at least a water intake test of 10 teaspoons and a lingual motor test is more accurate than screening protocols with only a single item (Intercollegiate Stroke Working Party, 2016). No single tool has achieved consensus as a standard screen (Daniels et al. 2012).

**Hypothesis 2 - *Using written guidelines for the first specialist clinical bedside swallow assessment will not be associated with incidence of pneumonia (Null hypothesis)***

Clinical bedside swallow assessments are undertaken by specialist trained healthcare professionals. A high degree of variability has been reported within the clinical bedside assessment process and in practice standardised assessments are less frequently used. Observation of practice has found that variability in reported practice is likely the result of a nuanced patient-centred assessment process characterised by iterative cycles of information gathering in order to generate and test clinical hypotheses and that there may be unintended negative consequences of

solely relying on data generated from standardised assessment tools (McAllister et al., 2020).

***Hypothesis 3 - Hospital Teams that insert Nasogastric Tubes (NGTs) overnight have increased risk of SAP compared to Hospital Teams that do not insert NGTs overnight.***

Evidence that nasogastric tube (NGT) placement increases risk of SAP is equivocal (Eltringham et al. 2019). Placement of NGT 'out of hours' has been the subject of a national patient safety alert advice. Nasogastric tubes should only be placed when senior support for placement and placement confirmation is readily available. The rationale for this was the greater risk of error by junior and less experienced staff confirming NGT placement in evenings and at night (NHS Improvement, 2016).

***Hypothesis 4 - Hospital Teams with a written oral care protocol will have reduced risk of incidence of SAP compared to those that do not have a written oral care protocol.***

Poor oral and dental hygiene have been identified as potential risk factors for SAP (Beavan, 2015) and lack of oral care has been identified as a significant issue by people affected by stroke (Eltringham et al. 2019). UK Clinical Guidelines recommend people with stroke, especially those who have difficulty swallowing or are tube fed, should have mouth care at least 3 times a day and staff should be trained in assessment of oral hygiene and selection of appropriate oral hygiene and cleaning agents, and provision of oral care routines. Latest European swallowing guidelines suggest oral health interventions should be considered in stroke patients.

## **Primary Outcome**

The primary outcome is association with stroke-associated pneumonia

## **Overview of Study design**

A mixed mode survey design comprising of a self-administered electronic survey with a secondary option of a postal survey. The sample frame was

Routinely Admitting, and Non-Routinely Admitting Acute Stroke Hospital Teams registered on the Sentinel Stroke National Audit Programme (SSNAP) register. The survey population was Speech and Language Therapy (SLT) Clinical Leads for Acute Stroke in Hyper/Acute Hospital Stroke Units in England and Wales. The total survey population were surveyed. Survey participants were asked to respond about practice on behalf of the Stroke Unit rather than as an individual practitioner.

### **Sampling plan**

Hospital teams were included if they were registered on the SSNAP register for October-December 2019 and had sufficient records/data to report and were an active Hyper/Acute Stroke Unit. One hundred and sixty-six hospital teams were included after exclusions. The SLT Clinical Lead for Acute Stroke or the most appropriate person was identified in each team to complete the survey on behalf of their Stroke Unit. A distribution list with their name and email address was created.

### **Response rate**

The response rate will be calculated as the number of completed surveys (1 survey per Hospital Team) divided by the survey population (N=166) multiplied by 100 to express a percentage.

### **Recruitment Process and access to the questionnaire**

Participants were directly contacted by email with an invitation letter, participant information sheet and provided a web link to the survey. A paper-based survey to be returned by a pre-paid stamped address envelope was offered on the last email reminder for those who had not already completed the web-based survey. The survey was a closed survey in that the hyperlink to the survey was only sent to the identified SLT Clinical Lead for Acute Stroke as only one response was requested from each hospital team. No participants requested a paper copy of the survey.

### **Survey administration**

The electronic survey was created using Qualtrics survey software and responses were automatically captured on the Qualtrics platform. Completed survey responses were exported from Qualtrics to SPSS software for statistical analysis.

The survey was distributed on 2/9/2020. The closing date for the survey was 2/10/2020. The hyperlink remained active for a few days after the closing date to allow for any late responders due to the COVID pandemic.

## **Statistical analyses**

Only completed surveys will be analysed. The survey data will be analysed using descriptive and inferential statistics. Descriptive statistics will include analysis of categorical and continuous data. Descriptive statistics of categorical variables will be frequency analysis i.e., percentage of the different categories within each variable. For example, proportion of Hospital Teams that are Routinely Admitting Teams and Non-Routinely Admitting Acute Teams. Categorical data will be visualised with bar and pie charts. The evaluation method for continuous data (incidence of pneumonia) will be mean and standard deviation to evaluate the dispersion of pneumonia incidence across the hospital teams and visualised using histograms.

Inferential statistics (linear regression analysis) will be used to test the hypotheses and explore if there is an association between the dependent variable (incidence of stroke-associated pneumonia) and independent binary variables: 1. Hospital Teams that use Water only dysphagia screening protocols (DSP) versus Hospital Teams that use water and other consistencies DSPs, 2. Hospital teams that use written guidelines for the first specialist clinical bedside swallow assessment versus Hospital teams that do not use written guidelines for the first specialist swallow assessment, 3. Hospital Teams that insert Nasogastric Tubes (NGTs) overnight have increased risk of SAP compared to Hospital Teams that do not insert NGTs overnight and 4. Hospital Teams with a written oral care protocol versus those do not have a written oral care protocol. Linear regression analysis will be visualised using Model Summary tables with Coefficients and 95% Confidence Intervals.

The proposed analysis for each variable is given in Table 1.

Table 1 – Proposed analysis for each variable

Variable	Data Source (s)	Values	Type of variable	Analysis approach	Methods for summarising data
Hospital Team	Survey Question #3 Please type the name of your hospital and select from the drop-down menu. SSNAP 2019 Team Centred 72-hour cohort data	1 = Routinely Admitting Team 2 = Non-Routinely Admitting Team	Categorical – Nominal - dichotomous	Descriptive statistics (frequencies) - Proportion of completed surveys for Routinely Admitting Team and Non-Routinely Admitting Acute Teams by SCN Region	Table
Written Dysphagia Screening Protocol	Survey Question #4 Does your stroke unit use a written dysphagia screening protocol (DSP)?	1 = Yes 2 = No	Categorical – Nominal - dichotomous	Descriptive statistics (frequencies) - Proportion answering yes or no	Bar chart
Standardised Dysphagia Screen	Survey Question # 5 Is the dysphagia screen a screen that was developed by your hospital or a standardised dysphagia?	1= Hospital Dysphagia Screen 2= Published Dysphagia Screen	Categorical – Nominal - dichotomous	Descriptive statistics (frequencies) - Proportion by selected choice	Bar chart
	Survey Question #7 Which published dysphagia screen is used?	Free text	Categorical - Nominal	Descriptive statistics (frequencies) – Proportion by named screen	Bar Chart
Person completing the screen	Survey Question #6 Is it mandatory that the person carrying out the dysphagia screen has been trained to use the dysphagia screening protocol?	1= Yes 2= No	Categorical - Nominal - dichotomous	Descriptive statistics (frequencies) - Proportion answering yes or no	Bar chart

	Survey Question #13 Which healthcare professional typically carries out the dysphagia screen? Please specify if more than one healthcare professional group is involved.	1= Stroke Nurse Specialist 2= Registered Nurse 3= Nursing Associate/Apprentice 4= Non-registered staff 5 = Other	Categorical - Nominal	Descriptive statistics (frequencies) – Proportion by selected choice	Pie chart/Free text
Components of the screen	Survey Question #8 Are the following involved in the dysphagia screening protocol?	1= Indirect Swallow Test 2= Oro-motor test 3= Indirect Swallow Test AND Oro-motor test 4 = Neither of the above	Categorical - Nominal	Descriptive statistics (frequencies) – Proportion by selected choice	Bar chart
	Survey Question #9 Does the dysphagia screening protocol only use water (Level 0 Thin Fluids) i.e., 100% water? SSNAP 2019 Patient Centred Post 72hr cohort data prescription of antibiotics for a newly diagnosed pneumonia	1= Yes 2= No  SPSS Recoded (dummy variables) 0=Yes 1=No	Categorical – Nominal - dichotomous  Dependent variable – outcome - incidence of SAP Independent variable – predictor – Water only DSPs versus water and other consistencies DSPs	Descriptive statistics (frequencies) - Proportion answering yes or no AND Inferential statistics (Linear Regression) Null hypothesis – There is no difference in incidence of pneumonia using a dysphagia screen that uses 100% water compared to water and other consistencies	Bar chart  Model Summary Table with coefficients and 95% Confidence Intervals
	Survey Question #10 What is the maximum amount of water given? Please indicate the maximum amount in millilitres (mls).	1=5, 2=10, 3=15, 4=20, 5=25, 6=50, 7=100, 8=150, 9=200	Categorical Ordinal	Descriptive statistics (frequencies)- proportion by selected choice	Bar chart

	Survey Question #11 Which International Dysphagia Diet Standardisation Initiative (IDDSI) levels are included in the dysphagia screening protocol?	1= Level 0 Thin, 2= Level 1 Slightly Thick, 3=Level 2 Mildly Thick, 4=Level 3 Moderately Thick, 5=Level 4 Puree, 6=Level 5 Minced and Moist, 7=Level 6 Soft & Bite Size, 8=Level 7 Regular Easy to Chew, 9=Level 7 Regular	Categorical – Ordinal	Descriptive statistics (frequencies) - Proportion by selected choice	Bar chart
	Survey Question #12 Which IDDSI level consistency do you screen with first?	1= Level 0 Thin, 2= Level 1 Slightly Thick, 3=Level 2 Mildly Thick, 4=Level 3 Moderately Thick, 5=Level 4 Puree, 6=Level 5 Minced and Moist, 7=Level 6 Soft & Bite Size, 8=Level 7 Regular Easy to Chew, 9=Level 7 Regular	Categorical – Ordinal	Descriptive statistics (frequencies) - Proportion by selected choice	Bar chart
Delays in dysphagia screening	Survey Question #14 Below is a list of reasons for delays in stroke patients being screened for dysphagia. How applicable are each of these reasons for delays in stroke patients being screened for dysphagia in your stroke unit?	1=Strongly applicable 2=Somewhat applicable 3=Somewhat less applicable 4=Strongly not applicable	Categorical – Nominal	Descriptive statistics - Likert Scale	Bar chart/Free text
Referral for a specialist swallow assessment	Survey Question #15 If the dysphagia screen identifies a dysphagia, is the patient referred for a clinical (bedside) swallowing assessment carried out by an appropriately trained healthcare professional?	1=Yes 2=No	Categorical – Nominal - dichotomous	Descriptive statistics (frequencies) - Proportion answering yes or no	Bar chart
	Survey Question #16 If the patient is not referred for a	1= Stroke Nurse 2= Registered Nurse	Categorical – Nominal	Descriptive statistics (frequencies) –	Pie chart/Free text

	specialist clinical (bedside) swallowing assessment which health professional group continues to review the patient's swallowing problem after the dysphagia screen?	3= Nursing Associate/Apprentice 4= Non-registered staff 5= Other		Proportion by selected choice	
Person completing the specialist swallow assessment	Survey Question #17 Which healthcare professional typically carries out the clinical (bedside) swallowing assessment?	1= Speech and Language Therapist 2= Not a SLT but an autonomous Health Professional trained at Specialist Level (as defined by the Inter-Professional Dysphagia Framework)	Categorical - Nominal	Descriptive statistics (frequencies) - Proportion by selected choice	Pie chart
Specialist swallow assessment	Survey Question #18 Does the stroke unit use a published dysphagia assessment for the clinical (bedside) swallowing assessment?	1=Yes 2=No	Categorical – Nominal - dichotomous	Descriptive statistics (frequencies) – Proportion answering yes or no	Bar chart
	Survey Question #19 Please state what published assessment is used e.g. The MANN Assessment of Swallowing Ability (MASA).	Free text		Free text	
	Survey Question #20 Do you use written guidelines about what should be included in a clinical (bedside) swallowing swallow assessment?	1=Yes – The Mann Assessment of Swallowing Ability 2 = Yes – Not the MANN but other written guidelines 3=No	Categorical – Nominal  AND Dependent variable –	Descriptive statistics (frequencies) – Proportion by selected choice AND Inferential statistics (Linear Regression)	Bar chart  Model Summary Table with

	SSNAP 2019 Patient Centred Post 72hr cohort data prescription of antibiotics for a newly diagnosed pneumonia	SPSS Recoded (dummy) variables 0=Yes 1=No	outcome - incidence of SAP Independent variable – predictor – Written guidelines (versus clinical reasoning and hypothesis generation)	Null hypothesis – Using written guidelines for the first specialist swallow assessment will not be associated with incidence of pneumonia	coefficients and 95% Confidence Intervals
Components of the specialist swallow assessment	Survey Question #21 In your Stroke Unit, what does the first clinical (bedside) swallow assessment typically involve?	1= PMH, 2= HPC, 3= Assessment of cognitive-communication status, 4= Assessment of respiratory status, 5= Cranial Nerve examination, 6=Cough reflex testing, 7= Assessment with oral intake 8= Assessment with postural strategies, 9= Assessment with swallowing manoeuvres, 10= Other	Categorical – Nominal	Descriptive statistics (frequencies) – Proportion by selected choice	Bar chart/Free text
	Survey Question #22 What International Dysphagia Diet Standardisation Initiative (IDDSI) levels are typically included in the first clinical (bedside) swallow assessment?	1=Level 0 Thin, 2= Level 1 Slightly Thick, 3= Level 2 Mildly Thick, 4=Level 3 Moderately Thick, 5= Level 4 Puree, 6=Level 5 Minced and Moist, 7=Level 6 Soft & Bite Sized, 8= Level 7 Easy to Chew, 9=Level 7 Regular	Categorical – Ordinal	Descriptive statistics (frequencies) - Proportion by selected choice	Bar chart
	Survey Question #23 Please describe what postural techniques are assessed? Examples include chin-down posture, chin-up posture, head	Free text		Free text	

	rotation (turn to side) and head tilt. These examples are not exhaustive.				
	Survey Question #24 Please describe what swallowing manoeuvres are assessed? Examples of include effortful swallow, Mendelsohn manoeuvre, supraglottic swallow and super-supraglottic swallow. These examples are not exhaustive.	Free text		Free text	
Delays in specialist assessment	Survey Question #25 Below is a list of reasons for delays in stroke patients receiving a clinical (bedside) swallowing assessment. How applicable are each of these reasons for delays in stroke patients receiving a clinical swallowing assessment in your stroke unit?	1=Strongly applicable 2=Somewhat applicable 3=Somewhat less applicable 4=Strongly not applicable	Categorical – Nominal	Descriptive statistics - Likert Scale	Bar chart/Free text
Instrumental Swallowing Assessments	Survey Question #26 Does your stroke unit have access to the following instrumental assessments of swallowing?	1= Videofluoroscopy (VFS) 2= Fiberoptic Endoscopic Evaluation of Swallowing (FEES) 3=Neither VFS or FEES 4=Both VFS and FEES	Categorical – Nominal	Descriptive statistics (frequencies) – Proportion by selected choice	Pie Chart
	Survey Question #27 For those patients where it is clinically indicated, would your stroke unit routinely use Videofluoroscopy	1=Yes 2=No	Categorical – Nominal - dichotomous	Descriptive statistics (frequencies) - Proportion answering yes or no	Bar Chart

Manchester  
Metropolitan  
University

	
within the first 7 days of a patient's admission? Survey Question #28 For those patients where it is clinically indicated, would your stroke unit routinely use FEES within the first 7 days of a patient's admission? Survey Question #29 For those patients where it is clinically indicated, would your stroke unit routinely use these assessments within the first 7 days of a patient's admission?
				
Management	
Survey Question #30 During the first 7 days of a stroke patient's admission, what treatment options are typically recommended on your Stroke Unit?
	
1= Diet and fluids modification, 2= Frazier Water Protocol, 3= Swallowing Manoeuvres, 4= Postural Techniques, 5= Sensory stimulation, 6= Tube feeding, 7=Oro-motor exercises, 8 =Pharmacological Management, 9=Electrical stimulation, 10= Biofeedback, 11= Other
	
Categorical - Nominal
	
Descriptive statistics (frequencies) – Proportion by selected choice
	
Bar chart/Free text

NGT Protocol	
Survey Question #31 Does your stroke unit have a written nasogastric tube (NGT) feeding protocol?
	
1=Yes 2=No
	
Categorical – Nominal - dichotomous
	
Descriptive statistics (frequencies) - Proportion answering yes or no
	
Bar chart

	Survey Question #35 Does your stroke unit have a written protocol for the maximum number of times the NGT can be inserted?	1=Yes 2=No	Categorical – Nominal - dichotomous	Descriptive statistics (frequencies) - Proportion answering yes or no	Bar chart
Time from decision to non-orally feed and feeding by NGT	Survey Question #32 In patients who are unable to maintain adequate nutrition and fluids orally, please indicate typically the number of hours from when the decision is taken to non-orally feed and the beginning of feeding by an NGT?	1=< 6 hours 2>= 6 - < 12 hours 3>= 12 - < 24 hours 4>= 24 - < 48 hours	Categorical - Nominal	Descriptive statistics (frequencies) - Proportion by selected choice	Bar chart
Confirmation of position of NGT	Survey Question #33 How does your stroke unit check the position of the NGT before starting feeding?	1= pH testing of NGT aspirate, 2= Chest radiography if no aspirate obtained or pH above recommended level, 3= Routinely perform chest radiography, 4= Other	Categorical - Nominal	Descriptive statistics (frequencies) - Proportion by selected choice	Pie Chart/Free text
Management strategies	Survey Question #34 In cases of inadvertent NGT removal, does your stroke unit typically use any of the following management strategies?	1= Mittens, 2= Nasal retention device, 3= 1:1 staff: patient supervision, 4=Other	Categorical - Nominal	Descriptive statistics (frequencies) - Proportion by selected choice	Pie Chart/Free text

Maximum number of NGTs	Survey Question #36 In case of inadvertent NGT removal, what is the maximum number of times reinsertion of the NGT is attempted in any patient?	1=Once, 2= Twice, 3= Three times, 4= If more than three, please state how many	Categorical – Ordinal	Descriptive statistics (frequencies) - Proportion by selected choice	Pie Chart/Free text
Overnight NGT insertion	Survey Question #37 Are NGTs inserted overnight? SSNAP 2019 Patient Centred Post 72hr cohort data prescription of antibiotics for a newly diagnosed pneumonia	1=Yes 2=No  SPSS Recoded (dummy) variables  0=Yes 1=No	Categorical – Nominal – dichotomous  Dependent variable – outcome - incidence of SAP Independent variable – predictor – Insertion of NGT overnight	Descriptive statistics (frequencies) - Proportion answering yes or no AND Inferential statistics (Linear Regression) Hypothesis – Hospital Teams that insert NGTs overnight have increased risk of SAP compared to Hospital Teams that do not insert NGTs overnight.	Bar chart  Model Summary Table with coefficients and 95% Confidence Intervals
Positioning during NGT feeding	Survey Question #38 Where 0 degrees is lying flat and 45 degrees is sat upright, what is the standard position in which the patient is positioned during NGT feeding?	1=0 degrees 2= > 0 - < 30 degrees 3= ≥ 30 - < 45 degrees 4= 45 degrees 5= Other (please state)	Categorical - Ordinal	Descriptive statistics (frequencies) - Proportion by selected choice	Bar chart/Free text

Oral Care Protocol	Survey Question #39 Does your stroke unit have a written oral care protocol?	1=Yes 2=No  SPSS Recoded (dummy) variables  0=Yes 1=No	Categorical – Nominal – dichotomous  Dependent variable – outcome - incidence of SAP Independent variable – predictor – written oral care protocol	Descriptive statistics (frequencies) - Proportion answering yes or no AND Inferential statistics (Regression) Hypothesis - Hospital Teams with a written oral care protocol will have reduced rates of incidence of SAP compared to those that do not have a written oral care protocol	Bar chart  Model Summary Table with coefficients and 95% Confidence Intervals
	Survey question #40 Is this protocol a hospital oral care protocol or a specific protocol written for the oral care of stroke patients on your unit?	1=Hospital oral care protocol, 2= Stroke oral care protocol	Categorical – Nominal - dichotomous	Descriptive statistics (frequencies) – Proportion by selected choice	Bar chart
Oral care provision in H/ASU	Survey question #41 Are there differences in oral care provision for patients in the hyper/acute stroke unit compared to those patients in other parts of the stroke pathway?	1=Yes 2=No	Categorical – Nominal - dichotomous	Descriptive statistics (frequencies) – Proportion answering yes or no	Bar chart

	Survey question #42 How is oral care provision in the hyper/acute stroke unit different to that provided post-acute phase stroke?	Free text		Free text	
Oral care provision for dysphagic patients	Survey question #43 Are there differences in oral care provision for patients with dysphagia?	1=Yes 2=No	Categorical – Nominal – dichotomous	Descriptive statistics (frequencies) – Proportion answering yes or no	Bar chart
	Survey question #44 If yes, please describe what differences there are in oral care provision for people with dysphagia compared to the provision for those people without dysphagia.	Free text		Free text	
Frequency of oral care for dysphagia patients	Survey question #45 How often each day is mouth care typically provided to people with dysphagia on the stroke unit?	1=Once, 2= Twice, 3= Three times, 4= Other please state	Categorical – Ordinal	Descriptive statistics (frequencies) - Proportion by selected choice	Pie Chart/Free text

Staff responsible for oral care	Survey question #46 Which staff group typically provide oral care? Please indicate if more than one group provide oral care.	1=Registered Nurse, 2= Nursing Associate or Nursing Apprentice, 3= Nonregistered staff e.g., clinical support worker and healthcare assistants, 4= SLT, 5= Occupational Therapist 6= Other - please state	Categorical – Nominal	Descriptive statistics (frequencies) – Proportion by selected choice	Pie chart/Free text
Training	Survey question #47 Do staff receive training in oral care?	1=Yes, 2=No	Categorical – Nominal – dichotomous	Descriptive statistics (frequencies) – Proportion answering yes or no	Bar chart
	Survey question #48 What type of training do staff receive?	1= Ward based training, 2= Classroom based training, 3= Online training, 4= Other - please describe	Categorical – Nominal	Descriptive statistics (frequencies) – Proportion by selected choice	Pie chart/Free text
	Survey question #49 Is the training staff receive specific to the oral care of stroke patients?	1=Yes, 2=No	Categorical – Nominal – dichotomous	Descriptive statistics (frequencies) – Proportion answering yes or no	Bar chart
Components of oral care	Survey question #50 What does oral care typically involve on the stroke unit?	1=Brushing of teeth and cleaning of gums with toothpaste 2= Brushing of teeth and cleaning of gums with chlorhexidine dental gel	Categorical – Nominal	Descriptive statistics (frequencies) – Proportion answering yes or no	Bar chart/Free text

		
3= Brushing of teeth and cleaning of gums using an electric toothbrush
 
4= Brushing of teeth and cleaning of gums using a suction toothbrush
 
5= Brushing of teeth and cleaning of gums with a manual toothbrush
 
6= Removal of excess secretions
 
7= Removal of dentures overnight
 
8= Brushing of dentures with water
 
9= Brushing of dentures and cleaning with soap
 
10= Brushing of dentures and cleaning with toothpaste
 
11= Brushing of dentures and cleaning with chlorhexidine dental gel
 
12= Soaking of dentures overnight in dental cleaning solution
 
13= Soaking of dentures overnight in water
 
14= Application of lip balm
 
15= Other - please describe
			
Variations in practice	
Survey question #51
 
The following question gives you the opportunity to tell us about any other variations in dysphagia screening, assessment and management during the
	Free text		Free text	

Manchester  
Metropolitan  
University

Stroke  
Association

	first 7 days of a patient's admission to your stroke unit.				
Sharing of protocols	Survey question #52 Please let us know if you would be happy to share your Trust protocols relating to the screening, assessment and management of stroke patients with dysphagia.	1= Yes 2= No	Categorical – Nominal – dichotomous	Descriptive statistics (frequencies) – Proportion answering yes or no	Bar chart

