## Method for analysing the data for incidence of stroke-associated pneumonia

Stroke-associated pneumonia (SAP) will be defined as the administration of antibiotics for a new clinical diagnosis of pneumonia in the first 7 days after admission as determined by the treating physician. SSNAP Patient Centred Post 72-hour quarterly data for Antibiotics for newly acquired pneumonia in the first 7 days from clock start will be used to calculate an annual 2019 pneumonia percentage for each team to measure the dispersion of the of pneumonia incidence across the teams.

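### The SD of raw team percentages includes binomial chance variation; a between-team SD net of chance should be reported beside it (low priority, descriptive only)

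*SAP*

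**What the plan says.** The section on the method for analysing incidence defines the outcome as "administration of antibiotics for a new clinical diagnosis of pneumonia in the first 7 days after admission as determined by the treating physician". For each patient this is a yes/no event. The same section uses quarterly audit data to "calculate an annual 2019 pneumonia percentage for each team to measure the dispersion" of incidence across the teams. The Statistical analyses section then names the summary: "mean and standard deviation to evaluate the dispersion of pneumonia incidence across the hospital teams and visualised using histograms".

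The SAP mentions no weighting by denominator, no variance correction, no random-effects model and no funnel plot. Its two examples of sensitivity analysis, regional response and the Covid period, do not bear on chance variation in team percentages.

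On team size, the SAP says only that the frame holds "Routinely Admitting, and Non-Routinely Admitting Acute Stroke Hospital Teams registered on the Sentinel Stroke National Audit Programme (SSNAP) register", that teams qualified if they "had sufficient records/data to report and were an active Hyper/Acute Stroke Unit", and that "One hundred and sixty-six hospital teams were included after exclusions". It gives no numeric minimum and no patients per team.

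**The concern.** Measuring dispersion is the purpose the SAP gives for the annual team percentage. A percentage based on n patients carries binomial error, so the percentages differ between teams even when every team has the same underlying incidence. The SD and histogram of raw percentages show the sum of the two sources and give the reader no means of separating them. Without the denominators, a reader cannot tell whether an extreme team is unusual or merely small.

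At stake is the reading of one descriptive result. If the SD is taken as the extent to which incidence truly differs between teams, it will be too large, and it will suggest more variation for practice differences to explain than there is.

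**Working it through.** The SAP states no SD, team size or power calculation, so there is no figure to reproduce. The check is a variance decomposition over a range of assumptions.

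**Inputs**
- Mean incidence p = 14%. The Research background calls pneumonia a "common post stroke infection affecting 14% of patients". This is a literature figure, not audit data; 8% was run as a check.
- Number of teams: 166, from the Sampling plan, used in the simulation only. Only completed surveys will be analysed, so the actual number may be smaller.
- Patients per team n and true between-team SD τ: not in the SAP, so assumed over a range.

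**Formula**, in squared percentage points:

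expected raw variance = τ² + (10,000·p(1−p) − τ²)/n

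With p = 0.14, 10,000 × 0.14 × 0.86 = 1,204.

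**Chance alone** (τ = 0): SD = √(1,204/n). This is 4.9 points at n = 50, 3.5 at 100, 2.5 at 200, 1.7 at 400 and 1.2 at 800. At 8% incidence it is 3.8 at n = 50 and 1.4 at n = 400.

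**Raw SD against the true SD**, p = 14%:

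| n per team | true SD τ | chance variance | raw SD | excess |
|---|---|---|---|---|
| 50 | 3 | (1,204 − 9)/50 = 23.90 | √32.90 = 5.74 | +91% |
| 100 | 3 | 1,195/100 = 11.95 | √20.95 = 4.58 | +53% |
| 200 | 3 | 1,195/200 = 5.98 | √14.98 = 3.87 | +29% |
| 400 | 3 | 1,195/400 = 2.99 | √11.99 = 3.46 | +15% |
| 800 | 3 | 1,195/800 = 1.49 | √10.49 = 3.24 | +8% |
| 400 | 5 | (1,204 − 25)/400 = 2.95 | √27.95 = 5.29 | +6% |
| 800 | 5 | 1,179/800 = 1.47 | √26.47 = 5.15 | +3% |

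**Unequal team sizes.** A beta-binomial simulation used 166 teams and 2,000 runs, with assumed lognormal sizes (median 400, log-SD 0.7, minimum 20). The corrected figure subtracts the mean of x(1−x)/(n−1) from the raw variance, where x is a team's observed proportion.

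| true SD | average raw SD | corrected SD |
|---|---|---|
| 0 | 1.95 | variance about 0 |
| 2 | 2.79 | 2.00 |
| 3 | 3.58 | 3.00 |
| 4 | 4.44 | 3.99 |
| 5 | 5.35 | 5.00 |

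The direction is therefore certain in expectation, and a simple subtraction removes the excess. The size depends on n and τ.

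**The case against.** The strongest reply is that the SAP lists this SD under descriptive statistics and never claims to estimate an underlying variation. As a description of the 2019 percentages in the analysed teams, a mean, SD and histogram are conventional and correct. That stands: the excess arises only when the SD is read as true differences between teams, although the stated aim of measuring dispersion of incidence invites that reading.

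It also stands that the effect may be trivial. Four quarters are combined into a year, teams needed sufficient data to be included, and with large teams and large true differences the excess is a few percent.

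Three stronger readings are tempting, and the SAP does not support them.
- A reader might infer that outcome variation between teams is the premise of the study, so that an inflated SD undermines it. The Research question section concerns variation in assessment and management. That is measured by the survey frequencies, not by this SD.
- A reader might infer that the unweighted mean of team percentages is an error. The hospital team is the unit of analysis, so that mean is a legitimate summary and matches the regression's dependent variable. It simply answers a different question from incidence among patients, and the SAP does not say that it will be compared with the 14%.
- A reader might infer that the hypothesis tests are compromised. They rest on a separate linear regression. No test uses this SD, and the coefficients are not biased by it.

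Nor can it be said that small teams will fill the tails of the histogram, because the SAP gives no distribution of team size.

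**Conclusion.** The point holds as a low-priority improvement to a descriptive figure. The raw SD is a correct account of the observed 2019 spread and an upwardly biased account of true between-team differences, and nothing in the SAP separates the two. At an assumed 14% incidence, the excess runs from about 3% (800 patients per team, true SD 5 points) through 15% (400, 3 points) to 53% (100, 3 points), and it would be larger still with smaller teams or a smaller true SD. These figures rest on assumed team sizes and true SDs; the documents cannot narrow the range.

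**What to change.** In the Statistical analyses section and the section on analysing incidence, keep the raw mean, SD and histogram and add:

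1. the distribution of patients per team;
2. pooled incidence, as total pneumonia cases over total patients;
3. a between-team SD net of binomial variance, from either the raw variance minus the mean of p(1−p)/n over teams (with n−1 in place of n when p is the observed proportion), or a random-intercept binomial model. State in advance that a negative difference is reported as zero;
4. a funnel plot of team percentage against team size.

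One sentence should say that the raw SD includes chance variation and that item 3 is the measure of differences between teams.

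The cost is a little more analysis. It also needs the numerators and denominators behind the percentages; the SAP names the quarterly audit data but does not say in what form they are held, so this should be confirmed. The between-team SD reported in item 3 will be smaller than the raw SD.
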